9.3 Analysis Sets, Subgroups, and Covariates

9.3.1 Analysis Sets

9.3.1.1 Full Analysis Set

The full analysis set consists of all subjects who were randomized in the study. Analysis of disposition, demographic and baseline characteristics, and important protocol deviations will utilize this analysis set.

9.3.1.2 Efficacy Analysis Set

The respective efficacy analysis set consists of a subset of subjects from full analysis set who receive at least 1 dose of investigational product and have a baseline value and at least 1 post baseline value for the endpoint of interest. Subjects will be analyzed according to their randomized treatment, regardless of the treatment received. Primary analysis of the efficacy endpoints will utilize the respective efficacy analysis set.

9.3.1.3 Safety Analysis Set

The respective safety analysis set will consist of all randomized subjects who received at least 1 dose of investigational product. Subjects will be analyzed according to the randomized treatment unless a subject has received the incorrect dose during the entire DBTP. Analysis for safety endpoints and summary of investigational product administration will utilize the respective safety analysis set.

9.3.2 Covariates

Model-adjusted analyses of efficacy endpoints will include the corresponding baseline value for the endpoint being analyzed, if applicable.

9.3.3 Subgroups

The primary and secondary endpoints will be analyzed in the following subgroups:

- Number of prior treatment failures (1, 2, and 3 or more treatment failures)
- Medication overuse status at baseline (yes vs no)

The subgroups will be re-examined for appropriateness and may be re-categorized (due to small sample size, for example, if there are < 10% of subjects within a subgroup) before unblinding.

9.3.4 Handling of Missing and Incomplete Data

Subjects may miss specific data points for a variety of reasons. In general, data could be missing due to a subject's early withdrawal from the study, a missed visit, or inability to evaluate an endpoint at a time point. For this study, efficacy endpoints will be collected via eDiary and subjects could miss entering several days of data in each monthly interval. The general procedures outlined below describe how missing data will be handled.

For the endpoints derived from daily diary during month 1 to 3, if at least 14 days of eDiary are collected in the monthly interval, then the monthly frequency measurements (eg, migraine days, headache days) will be prorated based on the number of days with available information.

Missing items in each clinical outcome assessment questionnaire will be handled based on the scoring algorithm for each assessment.

Missing data after above methods will either be handled by the linear mixed effects model under missing-at-random assumption or imputed as non-responders for binary endpoint.

Missing data in safety data will not be imputed.

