- 109 Must be the same migraine type as the initial screening period (ie, if a subject meets HFEM criteria in the 3 months prior to screening, then the subject must meet HFEM criteria during baseline).
- 110 Must have ≥ 4 migraine attacks of at least moderate severity during the baseline period.
- 111 Demonstrated at least 80% compliance with the daily eDiary during the baseline period.
- 112 Subject must treat qualifying migraine attacks with the same oral triptan as used during run-in period using 1 of the specified 4 oral triptans from inclusion criteria 107.

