9.2 Sample Size Determination

A total sample size of 576 subjects (288 subjects per group including 10% dropouts) provides at least a 90% power for the primary efficacy hypothesis. The statistical power for secondary efficacy hypotheses ranges from 81% to > 99% (Table 9-1).

Table 9-1. Sample Size Assumptions and Statistical Powers for Primary andSecondary Efficacy Endpoints for a Total Sample Size of 576 Subjects Including a10% Attrition Rate due to Dropout

Hypothesis	Assumed Treatment Effect (Common SD)	Power
Primary:	- 16.7 (50)	96%
Change from baseline in mean monthly hours of at least moderate headache pain intensity over months 1, 2, and 3		
Secondary: Change from baseline in mean monthly		
MFIQ physical function domain score over months 1, 2, and 3	-9.2 (18.0)	> 99%
MFIQ usual activities domain score over months 1, 2, and 3	-7.5 (19)	> 99%
MFIQ emotional function domain score over months 1, 2, and 3	-11.5 (22)	> 99%
MFIQ social function domain score over months 1, 2, and 3	-6.9 (20)	97%
Average duration of at least moderate migraine pain intensity in migraine attacks occurring over months 1, 2, and 3 ^a	-2.0 (8)	81%
Average peak migraine pain intensity over months 1, 2, and 3	-0.11 (0.44)	81%

MFIQ = Migraine Functional Impact Questionnaire.

Note: All power calculations are based on a 2-sided significance level of 0.05. The assumed treatment effects and common standard deviations are derived or chosen from a subset of placebo-treated and erenumab-140 mg-treated subjects in erenumab Study 20120296 with high-frequency episodic migraine (ie, 7 to 14 monthly migraine days) and having at least 4 moderate-to-severe migraine attacks at baseline. ^a If a subject did not have any migraine attacks in a given month, the duration of at least moderate migraine pain intensity was counted as 0.

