- A headache with acute headache medications (migraine-specific or not) taken during the headache (start time and end time inclusive) with any length of duration, or
- An aura during which an acute migraine-specific medication is administered

Headache Day

A calendar day (00:00 to 23:59) in which the subject experiences \geq 1 qualified headache

Qualified Migraine Headache

A qualified migraine headache should meet at least one of the following criteria:

- A headache of duration ≥ 30 minutes, and meeting ≥ 1 of the following criteria (a and/or b):
 - a) \geq 2 of the following pain features:
 - Unilateral
 - Throbbing
 - Moderate to severe (based on the 3-level categorical pain severity)
 - Exacerbated with exercise/physical activity
 - b) \geq 1 of the following associated symptoms:
 - Nausea
 - Vomiting
 - Photophobia and phonophobia
- A headache during which an acute migraine-specific medication is administered regardless of the headache duration, pain features, and associated symptoms
- An aura during which an acute migraine-specific medication is administered

Migraine Day

A calendar day (00:00 to 23:59) in which the subject experiences \geq 1 qualified migraine headache

Migraine-free Day

A calendar day (00:00 to 23:59) **of a diary day** in which the subject does not experience any headache and aura, photophobia, phonophobia, and nausea/vomiting, **and does**

not take any acute headache medication

Diary Day

A calendar day (00:00 to 23:59) with complete headache, aura, and acute headache medication data recorded **via daily evening diary**

Information Day

A calendar day (00:00 to 23:59) which is either a headache day or a diary day

Migraine Attack in M-DBTP

A migraine attack is an episode of any qualified migraine headache. The following rules will be used to distinguish an attack of long duration from 2 attacks, or to distinguish between attacks and relapses:

- A migraine attack that is interrupted by sleep, or temporarily remits, and then recurs within 48 hours (recurrence time headache start time ≤ 48 hours) will be counted as 1 attack
- An attack treated successfully with medication but with relapse within 48 hours (recurrence time headache start time ≤ 48 hours) will be counted as 1 attack

Triptan-treated Migraine Attack in M-DBTP

A migraine attack with triptan taken during the attack (start time and end time inclusive)

Headache Pain Intensity (evaluated by NRS) in M-DBTP

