Worst or peak pain intensity collected on a headache ranges from 0 to 10 with a higher score indicating more severe pain.

Pain intensity is reported when the headache end time is reported or in an evening diary on a daily basis for an ongoing headache. Therefore, there can be multiple pain intensity values reported for a headache that lasts for multiple days. In some circumstances, a headache which starts and ends on the same day may also have up to 2 pain intensity values reported when the headache ends after evening diary completion: 1) pain intensity is reported in the evening diary for the period between headache start time and diary completion time; 2) pain intensity is reported either in any-time diary or the next day's evening diary for the period between previous diary completion time and headache end time. The NRS headache pain intensity will be used to assess the monthly average peak pain intensity.

Headache Pain Intensity (3-level)

Worst or peak pain intensity collected on a headache in 3 levels (mild, moderate or severe) followed by the NRS pain intensity question when the preceding NRS headache pain intensity is reported to be \geq 4, worst or peak pain intensity (3 levels) is set as mild if NRS headache pain intensity is reported to be <4.

Duration of Headache With at Least Moderate Pain Intensity

Duration of headache with at least moderate pain intensity (in hours and minutes) will be collected only when "Moderate" or "Severe" intensity is reported based on the 3-level headache pain intensity scale.

Monthly Migraine Days (MMD)

Number of migraine days during one monthly interval as defined below.

Number of Diary Days in a Monthly Interval	Monthly Migraine Days
• ≥14 days	Prorate to 28-day equivalent without rounding Number of observed migraine days*28/number of (diary days or migraine days) within each monthly interval
• < 14 days	Set to missing

Monthly Headache Days (MHD)

Number of headache days during one monthly interval as defined below.

Number of Diary Days in a Monthly Interval	Monthly Headache Days
● ≥ 14 days	Prorate to 28-day equivalent without rounding
	Number of observed headache days*28/number of information days
	Note: An information day is either a headache day or a diary day.
• < 14 days	Set to missing

Monthly Hours of at Least Moderate Headache Pain Intensity

Number of Diary Days in a Monthly Interval	Monthly Hours of at Least Moderate Headache Pain Intensity

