• ≥ 14 days	Prorate to 28-day equivalent without rounding Sum of hours of headaches with at least moderate pain intensity *28/number of (diary days or days with headache pain intensity) within each monthly interval
• < 14 days	Set to missing

Monthly Hours of at Least Moderate Headache Pain Intensity of Qualifying Oral Triptan Treated Migraine Attacks

Number of Diary Days in a Monthly Interval	Monthly Hours of at Least Moderate Headache Pain Intensity of Qualifying Oral Triptan Treated Migraine Attacks
• ≥14 days	Prorate to 28-day equivalent without rounding Sum of hours of at least moderate pain intensity of qualifying oral triptan treated migraine attacks *28/number of (diary days or migraine days) within each monthly interval
• < 14 days	Set to missing

Monthly Average Duration of at Least Moderate Pain Intensity in Migraine Attacks

Number of Diary Days in a Monthly Interval	Monthly Average Duration of at Least Moderate Pain Intensity in Migraine Attacks
• ≥14 days	Sum of all the reported duration with at least moderate headache pain intensity within an attack divided by number of attacks in each month If there is no migraine during the monthly interval, then the monthly average duration will be set to 0.
• < 14 days	Set to missing

Monthly Average Duration of at Least Moderate Pain Intensity in Qualifying Oral Triptan Treated Migraine Attacks

Number of Diary Days in a Monthly Interval	Monthly Average Duration of at Least Moderate Pain Intensity in Qualifying Oral Triptan Treated Migraine Attacks	
• ≥ 14 days	Sum of all the reported duration with at least moderate headache pain intensity within a qualifying oral triptan-treated attack divided by number of qualifying oral triptan-treated attacks in each month;	
	If there is no migraine during the monthly interval, then the monthly average duration will be set to 0.	
• < 14 days	Set to missing	

Monthly Average Peak Migraine Pain Intensity

Number of Diary Days in a Monthly Interval	Monthly Average Peak Migraine Pain Intensity
• ≥14 days	Sum of observed highest pain intensity scores (NRS) per migraine day divided by total number of migraine days with at least one measure of NRS; If there is no migraine day with NRS during the monthly interval, then the monthly average peak migraine pain intensity will be set to 0.
● <14 days	Set to missing

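### The 14-diary-day minimum lets a sparsely recorded month score 0, the best possible value, on average attack duration (step 3) and average peak pain (step 4)

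*Protocol*

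**What the plan says.** Protocol 9.3.4 states the diary minimum for one kind of variable: "if at least 14 days of eDiary are collected in the monthly interval, then the monthly frequency measurements". It gives examples and says what happens to the days not seen: "eg, migraine days, headache days) will be prorated based on the number of days with available information".

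SAP 5.1.1 uses the same 14-day cut for two averages that are not prorated. Both sit in the alpha-controlled sequence of SAP 9.1.

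- **Step 3, monthly average duration.** In the row for 14 or more diary days: "If there is no migraine during the monthly interval, then the monthly average duration will be set to 0".
- **Step 4, monthly average peak pain.** In the same row, the value is also 0 under this condition: "If there is no migraine day with NRS during the monthly interval".

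Neither zero carries a stricter completeness condition. A diary day is one "with complete headache, aura, and acute headache medication data recorded" through the evening diary. The pain scale "ranges from 0 to 10 with a higher score indicating more severe pain", so 0 is its floor.

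Protocol Table 9-1, footnote a, gives the zero rule for duration only: "If a subject did not have any migraine attacks in a given month", the duration counts as 0. It says nothing about diary completeness. At baseline the bar is higher. Inclusion 111 reads "Demonstrated at least 80% compliance with the daily eDiary during the baseline period", and inclusion 110 asks for at least 4 attacks of at least moderate severity. SAP 9.5.1 rules out sensitivity analyses for the primary and secondary endpoints.

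**The concern.** Fourteen diary days can support an average over the attacks that were recorded. They cannot show that a 28-day month held no attack. For a count, proration deals with the unseen days. For these two averages nothing does, and the absence of a record is read as absence of migraine. Below, a month scored 0 although a migraine occurred is called a false zero.

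The error runs one way. With at least 4 moderate or severe attacks and at least 80% compliance required at baseline, an eligible subject has no false zero there. Every false zero therefore falls on treatment and counts as the largest possible improvement.

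Step 4 has a second route to the same error. A month with migraine headache but no pain score is also set to 0, although the pain is unknown.

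**Working it through.** **Inputs from the documents.** 288 per arm with 10% dropout; two-sided 0.05; step 3 effect -2.0 (SD 8); step 4 effect -0.11 (SD 0.44); 14-day cut; 80% baseline bar (0.8 x 28 = 22.4, so 23 of 28 days).

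**Assumptions, because the documents give no figures.** Attacks per 28 days on treatment of 2 to 5; 10% of months with 14 to 22 diary days, evenly spread; mean peak pain 6 (range 5 to 7); mean duration 6 to 12 h; equal diary completion in both arms; nothing captured on days without an evening diary.

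**1. The plan's own figure.** n = 288 x 0.9 = 259 per arm. Both endpoints have effect/SD = 0.25. z = 0.25 / sqrt(2/259) = 2.845, and power = Phi(2.845 - 1.960) = 81.2%. The stated 81% reproduces for both steps.

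**2. Chance of a false zero.** With Poisson attacks at rate L per 28 days, P(none in n days) = exp(-L x n/28). With strong between-subject variation (gamma shape 2) it is (1 + L x n/56)^-2. The excess of zeros is P(none in n days) - P(none in 28 days).

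| L | Poisson, none in 28 d | Poisson, none in 14 d | Excess at 14 d | Mean excess, 14-22 d: Poisson | Same: gamma |
|---|---|---|---|---|---|
| 2 | 13.5% | 36.8% | 23.3 | 14.6 | 12.4 |
| 3 | 5.0% | 22.3% | 17.3 | 10.1 | 10.3 |
| 4 | 1.8% | 13.5% | 11.7 | 6.3 | 8.4 |

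(Excess in percentage points.) The excess grows as attacks become fewer. Equal diary completion therefore still gives more false zeros to the arm with fewer attacks.

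**3. Shift in the step 4 difference, 4 versus 3 attacks.** Shift = sparse share x difference in mean excess x mean pain.

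- Poisson: 0.10 x (0.1012 - 0.0634) x 6 = 0.023.
- Gamma: 0.10 x (0.1031 - 0.0841) x 6 = 0.011.

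This is about 10% to 21% of 0.11. For mean pain 5 to 7 the range is 0.010 to 0.026. At 5 versus 4 attacks the shift is 0.009 to 0.015, and at 3 versus 2 it is 0.013 to 0.027. It scales with the sparse share.

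**4. Shift in step 3.** From 0.10 x 0.0190 x 6 = 0.01 h to 0.10 x 0.0378 x 12 = 0.05 h, against 2.0 h. Negligible.

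**5. Effect of a stricter bar.** At 23 diary days and L = 3, P(none) is 8.5%. The excess falls from 17.3 points at 14 days to 3.5.

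**6. Deleting sparse months only when no migraine was recorded.** Of all months at L = 3, the current rule gives a zero excess of 0.10 x 10.1 = 1.0 point. Under selective deletion, the zero share among kept months is 0.9 x P28 / (0.9 + 0.1 x (1 - S)), where P28 is the chance of no attack in 28 days and S the mean chance of no recorded attack in a sparse month.

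- Poisson: P28 = 0.0498, S = 0.151, share 4.55%, a deficit of 0.4 point.
- Gamma: P28 = 0.16, S = 0.263, share 14.8%, a deficit of 1.2 points.

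The 4-versus-3 shift in step 4 then reverses to about +0.02. That remedy swaps one bias for another.

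**The case against.** **Days without an evening diary are not always unobserved.** SAP 5.1.1 provides any-time entries around the clock, and pain up to the end of a headache can be entered later. This stands, and it makes the shifts above upper bounds under their assumptions.

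**Step 4 counts migraine days, not attacks.** If 14 of 28 days are observed at random, the chance of missing every migraine day is 4.9% with 4 such days and 0.3% with 7. This stands in part: migraine days cluster within attacks, which raises these figures again.

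**Other analyses already show the effect of zeros.** Both endpoints are repeated in months with at least 1 attack, and SAP 8.5 and 8.6 allow ad hoc outlier checks and a non-parametric method. These help, but the restricted versions also drop truly migraine-free months and lie outside the test sequence. The ad hoc checks do not address diary completeness.

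**A reader might infer a large power loss.** Adding 1.0% false zeros to an SD held at 0.44 gives sqrt(0.44^2 + 36 x 0.0101 x 0.9899/3) = 0.56, and step 4 power of about 61%. The documents do not support this. The same Poisson model already has 5.0% true zero months, which by the same formula give an SD of 0.87 and 30% power before any false zero, and 27% after. The model and the planned SD do not fit together, so the 61% has no sound basis.

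**A reader might also infer a conflict with footnote a.** There is none: the footnote is silent on how an attack-free month is established.

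**Conclusion.** The defect holds in the text. A minimum stated for prorated counts is used to declare a month migraine-free on two unprorated confirmatory averages, and the resulting error can only look like improvement. For step 4, an unknown pain score is also turned into 0.

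The likely size is modest. Under the stated assumptions it is a shift of about 0.01 to 0.02 in the step 4 difference, where the assumed effect is only 0.11, and next to nothing in step 3. The primary endpoint is prorated and the MFIQ scores do not come from the daily diary, so steps 1 and 2 are untouched.

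One might conclude that the rule favours erenumab. That is so only if diary completion is similar in both arms and erenumab has fewer attacks. If completion differs by arm, the shift can go either way, and the documents give no completion data. The point deserves a change before unblinding because it is cheap and the plan has no prespecified check for it.

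**What to change.** Before unblinding:

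1. Add to SAP 5.1.1 and 9.5.1 a prespecified analysis of the step 3 and step 4 endpoints in which every month, with or without a recorded migraine, needs diary days on at least 80% of its interval. Otherwise the month is missing and left to the mixed model. Report it beside the 14-day version, or make it the main rule for these two endpoints. Amend the SAP 9.5.1 statement on sensitivity analyses to match.
2. Apply the bar to diary days, not information days. Information days include headache days and so depend on the outcome.
3. Do not set sparse months to missing only when no migraine was recorded.
4. For step 4, set a month with migraine headache days but no pain score to missing, not 0. Treated aura without headache has no pain to rate and need not be covered by this change.
5. State in protocol 9.3.4 or SAP section 10 that the 14-day cut also governs averages, if it is kept.

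The cost is a few lines of text and programming, with no new data. Some sparse months are lost. A subject leaves the model only if all three months become missing. If that happens to 2% of subjects (253.8 per arm), power for either step falls from 81.2% to 80.4%; at 5% it is 79.2%. These loss rates are assumptions. The 80% bar reduces false zeros but does not remove them, and it relies on diary gaps being unrelated to unrecorded migraine.

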9.4 Statistical Analyses

The statistical analysis plan (SAP) will be developed and finalized before database lock. Below is a summary of the timing and methods for the planned statistical analyses. To preserve study integrity, the final analysis will be conducted and reported following the end of study, as defined in Section 4.4.1.

9.4.1 Planned Analyses

9.4.1.1 Primary Analysis

The primary analysis (or final analysis since there is only 1 milestone analysis for this study) will occur after all subjects have completed their week 16 visit (or discontinued from the study). The DBTP treatment assignment will be unblinded and all efficacy and safety analyses will be conducted and reported by the DBTP treatment group.

9.4.2 Methods of Analyses

9.4.2.1 General Considerations

Summary statistics will be computed by treatment group and visit. For continuous endpoints, the following descriptive statistics will be computed: number of observations, means, medians, standard deviations, standard errors, first and third quartiles, minimums and maximums, and 2-sided 95% CIs of the means (CIs will be provided for efficacy endpoints only). For categorical endpoints, the summaries will contain the number and percentage of subjects in each category.

The primary analysis method utilizing a repeated measures linear mixed effects model will include all observed data regardless of treatment adherence.

A sequential testing procedure will be used to maintain the family-wise type 1 error $\alpha = 0.05$ between the primary and secondary endpoints following the prespecified order below. An endpoint will only be tested for statistical significance if the endpoint tested in the previous step is statistically significant at 2-sided significance level of 0.05.

1. Primary endpoint: change from baseline in mean monthly hours of at least moderate headache pain intensity over months 1, 2, and 3

- 2. Secondary endpoints: change from baseline in mean monthly function domain score over months 1, 2, and 3, as measured by the MFIQ using the Hochberg procedure
 - Impact on physical functioning
 - Impact on usual activities
 - Impact on emotional functioning
 - Impact on social functioning
- Secondary endpoint: change from baseline in mean monthly average duration of at least moderate pain intensity in migraine attacks occuring over months 1, 2, and 3 (migraine attacks as defined in Section 11.1)
- 4. Secondary endpoint: change from baseline in mean monthly average peak migraine pain intensity over months 1, 2, and 3, as assessed by the 11-point NRS

Endpoint	Statistical Analysis Methods
Primary	The primary endpoint will be analyzed using a linear mixed effects model including treatment group, baseline value, scheduled visit, and the interaction of treatment group with scheduled visit, without any imputation for missing data.
Secondary	The secondary endpoints will be analyzed using a linear mixed effects model including treatment group, baseline value, scheduled visit, and the interaction of treatment group with scheduled visit, without any imputation for missing data.
Exploratory	Detailed primary analysis method for exploratory endpoints will be described in the SAP.

